# If this results in a substantial improvement of the NW performance

Figure 2: NightWatch around upper arm.

Figure 3: alarm system (left) and NightWatch (right).

[figure not shown]

Figure 4: Overview of SDDs in study.

#### 4. STUDY POPULATION

#### 4.1 Population (base)

Around 20,000 children carry the diagnosis of epilepsy in the Netherlands [23]. Most children with severe or difficult to treat epilepsy are under specialized epilepsy care in SEIN, Kempenhaeghe or UMCU. This study will include 60 children with refractory epilepsy (≥1 major nocturnal seizure per week) from one of the above epilepsy care facilities. There will be no restrictions on seizure etiology.

#### 4.2 Inclusion criteria

In order to be eligible to participate in this study, a subject must meet all of the following criteria:

- Age 4-16 years
- Diagnosis of refractory epilepsy with ≥1 major nocturnal motor seizure per week.
- Treated at one of the following epilepsy centers: SEIN, Kempenhaeghe or UMCU.
- Written informed consent by legal representatives (mostly parents) and also by the subject when aged ≥12 years and capable of signing informed consent.

#### 4.3 Exclusion criteria

A potential subject who meets any of the following criteria will be excluded from participation in this study:

- Intensive non-epileptic movement patterns such as severe choreatiform movements, intensive sleep walking, or frequent night terrors (> 1/week).
- Minor motor seizures only, i.e. non-generalized or short (< 10 sec.) tonic seizures or isolated myoclonias that are self-limited and do not require intervention.
- Presence of a pacemaker or cardiac arrhythmias that may generate false alarms (e.g. supraventricular tachycardia).
- Inability to comply to the trial procedure.
- Skin characteristics (e.g. dark skin color or tattoo) that may affect photoplethysmography and thereby influence performance of the NightWatch.
- Dependence on another SDD (e.g. Emfit or saturation monitor). Simultaneous use of a baby phone (or other types of microphones) is permitted.
- Subjects who are not sleeping alone in the bed (i.e. co-sleeping in the
  parents'/guardians' bed influences the remote SDD). We do not allow subjects and
  parents/guardians to change their sleeping habits for the duration of the study only.

# 4.4 Sample size calculation

If 60 subjects are monitored for two months at minimal seizure frequency of 1 per week we will likely obtain around 540 seizures. To assess the diagnostic performance of the NightWatch this sample size seems sufficient. The detection algorithms aim to reach a sensitivity of 80% and a PPV of 50%. A sample size of 384 would be sufficient to reach a confidential interval of 5% (given a confidence level of 95%) [24]. A sample size of 60 subjects will allow us to intercept a drop-out rate of approximately 30% for the feasibility study.

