#### 1. INTRODUCTION AND RATIONALE

Epilepsy impacts ~180.000 people in the Netherlands [1]. Despite advances in treatment, one third of all people with epilepsy continue to have seizures [2] that adversely affect quality of life (QoL) [3,4]. Poor seizure control is the major determinant of impaired QoL. Seizures impact not only individuals with epilepsy but also their guardians [5-7] as seizures are (1) unpredictable, (2) may cause loss of control and (3) cause life threatening situations, including injuries, status epilepticus and sudden unexpected death in epilepsy [8]. Convulsive seizures carry the greatest mortality risk, particularly those occurring at night, as these are often unwitnessed [9]. Childhood epilepsy has also a severe impact on parental QoL [10] and monitoring devices can help to improve parental anxiety levels, quality of sleep, and QoL [11]. Various non-EEG based signals have been assessed for the detection of potentially dangerous seizures [12]. Seizure detection devices (SDDs) have had, however, limited impact on epilepsy care so far. Barriers to SDD implementation include lack of external validation and high rate of false alarms. Most SDDs rely on a single modality. This approach likely explains limited sensitivity and specificity [12]. Previous studies validated multimodal algorithms for wearable sensors (accelerometry & heart rate) and demonstrated the feasibility of remote sensors (audio & video) to detect seizures [13-17]. Preliminary results indicate that the performance of the NightWatch is superior to a commonly used bed sensor, the Emfit. Our multicenter prospective trial in a residential population of adults with epilepsy and learning disabilities (LICSENSE trial, NTR4115) shows a median sensitivity per person of 85.7% with a positive predictive value of 49.3% and a median false negative alarm rate of 0.04 per person per night [18]. The interim analysis of our recent trial in 21 children (LICSENSE phase III) indicated that the algorithms needed an adjustment as in children higher heart rates are more common and less specific features for epilepsy appear thus increasing the number of false alarms. In response we updated our algorithm (with less emphasis on heart rate changes and more weight on movement changes). This approach still reach 80% sensitivity and 50% PPV in the majority (80%) of subjects (adults and children). This current prospective home-based trial is needed as a final validation step for the new algorithm in children and to evaluate feasibility of NightWatch. Former trials were performed without actual alarms. The current trial also enables us to get insight in the real life situation of children and their parents/guardians by focusing on feasibility. The literature has so far only discussed these needs with questionnaires but without insight into the home situation [19].

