#### **10 STATISTICAL ANALYSIS**

#### 10.1 Primary study parameter(s)

Performance of the algorithms (sensitivity, positive predictive value, false alarm rate and % time with valid signal allowing proper detection) will be expressed using descriptive statistics.

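### Section 4.4 justifies the trial size with seizures pooled over children as independent units, while earlier performance is given per person and section 10.1 does not say which unit the primary results use

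*Combined protocol and SAP*

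**What the plan says.** Section 4.4 (Sample size calculation) gets its number of observations by multiplying children by a weekly rate: "If 60 subjects are monitored for two months at minimal seizure frequency of 1 per week we will likely obtain around 540 seizures". It states the performance aim without a unit, "The detection algorithms aim to reach a sensitivity of 80% and a PPV of 50" per cent, and gives 384 as enough for a 5-point interval at 95% confidence. The only statement there about the number of children concerns another part of the study: "A sample size of 60 subjects will allow us to intercept a drop-out rate of approximately 30% for the feasibility study".

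Section 1 (Introduction and rationale) uses the person as the unit. The earlier adult trial is cited as showing "a median sensitivity per person of 85.7" per cent. The updated algorithm is said to reach "80% sensitivity and 50% PPV in the majority (80%) of subjects", in a group of adults and children. The same section presents the current trial as the last validation step for that algorithm in children.

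Section 4.2 requires at least one major nocturnal motor seizure per week and sets no maximum. Section 10.1 says of the four primary performance measures only that they "will be expressed using descriptive statistics". It names no unit, weighting or interval method.

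**The concern.** A pooled sensitivity weights each child by the number of seizures, and a pooled PPV by the number of alarms. A per-child median gives each child equal weight. If seizure counts differ widely and detection differs between children, these summaries answer different questions, and only the second is like the per-person results in section 1. The plan gives a precision for the first kind of summary, reports its background evidence in the second, and leaves the choice open in section 10.1.

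Two things are at stake. The unit could be chosen after the data are seen. And the stated precision could be attached to a figure that it does not describe: seizures within one child tend to resemble each other, so 540 seizures from 60 children carry less information than 540 independent ones.

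**Working it through.** **Inputs from the documents.** 60 children, two months, at least 1 seizure per week, about 540 seizures, 384 required, 5 points, 95% confidence, aims of 80% sensitivity and 50% PPV, and 30% drop-out (all section 4.4); no upper limit on seizure rate (section 4.2). **Not in the documents:** the distribution of seizure counts and the within-child correlation (ICC). I assume an ICC range of 0.05 to 0.5.

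**1. The plan's own figures.** 60 × 9 weeks × 1 = 540. (With 61 days, 60 × 61/7 = 523; the text says around.) The required number is z²p(1−p)/h² = 1.96² × 0.5 × 0.5 / 0.05² = 384. Both figures reproduce. The formula assumes independent observations and the least favourable proportion, 50%. At p = 0.8, the sensitivity aim, it gives 1.96² × 0.8 × 0.2 / 0.05² = 246.

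**2. Clustering with equal counts.** With 9 seizures per child the design effect is 1 + (9 − 1) × ICC, and the effective number is the total divided by it. Half-widths are 1.96 × √(p(1−p)/effective number). The rows for 42 children assume that the 30% who drop out contribute no seizures (42 × 9 = 378).

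| Children | ICC | Effective number | Half-width at 80% (points) | Half-width at 50% (points) |
|---|---|---|---|---|
| 60 | 0 | 540 | 3.4 | 4.2 |
| 60 | 0.05 | 386 | 4.0 | 5.0 |
| 60 | 0.1 | 300 | 4.5 | 5.7 |
| 60 | 0.3 | 159 | 6.2 | 7.8 |
| 60 | 0.5 | 108 | 7.5 | 9.4 |
| 42 | 0 | 378 | 4.0 | 5.0 |
| 42 | 0.05 | 270 | 4.8 | 6.0 |
| 42 | 0.1 | 210 | 5.4 | 6.8 |
| 42 | 0.3 | 111 | 7.4 | 9.3 |
| 42 | 0.5 | 76 | 9.0 | 11.3 |

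With equal counts the pooled value equals the mean of the per-child values, so the table also gives the precision of mean per-child sensitivity. It does not give the precision of a median.

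Break-points for 60 children: below 384 when ICC > (540/384 − 1)/8 = 0.051; below 246 when ICC > (540/246 − 1)/8 = 0.149. For 42 children, 378 is already just under 384, and the 246 limit is crossed at (378/246 − 1)/8 = 0.067.

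The denominator of PPV is alarms, not seizures. If both aims were met there would be 540 × 0.8 / 0.5 = 864 alarms, so the count of 540 bears directly on sensitivity only.

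**3. Unequal counts (illustration; all rates assumed).** Take 54 children at 1 seizure per week and 6 at 1 per night, for 61 nights. The six supply 6 × 61 = 366 seizures, the others 54 × 61/7 = 470.6. The share of the six is 366/836.6 = 43.75%.

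- Sensitivity 95% in the six and 75% in the rest: pooled 0.4375 × 0.95 + 0.5625 × 0.75 = 83.75%; median child 75%; mean child (6 × 95 + 54 × 75)/60 = 77%.
- Sensitivity 65% in the six and 85% in the rest: pooled 0.4375 × 0.65 + 0.5625 × 0.85 = 76.25%; median child 85%; mean child 83%.

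Pooling can therefore flatter or understate. Unequal counts also raise the design effect, because the cluster size 9 is replaced by Σm²/Σm = (6 × 61² + 54 × 8.714²)/836.6 = 31.6. At ICC 0.1 the design effect is 1 + 30.6 × 0.1 = 4.06, and 836.6 seizures are worth about 206.

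**4. Share of children observed to reach 80%.** With 9 seizures, 7/9 is 78%, so 8 detections are needed. The probability of at least 8 of 9 is 9p⁸(1−p) + p⁹: 0.44 for a true sensitivity of 80% and 0.77 for 90%. Even if every child truly had 90%, fewer than 80% of children would be expected to reach the mark, and requiring 50% PPV as well can only lower the share. The observed share is biased as a measure of how many children truly reach 80%.

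**The case against.** A reader might infer that the trial will report a pooled headline figure, and that a few children with frequent seizures could carry it past 80% to a declared success. The documents do not support that. Section 10.1 commits to neither summary; counting events in a sample size calculation does not fix the reported estimate; and the 80% and 50% are aims, with no hypothesis or pass rule.

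Nor is a per-child endpoint formally defined. The 80%-of-subjects result in section 1 is background on a mixed group of adults and children, and the aim in section 4.4 names no unit. Per-child performance is produced in any case: under sections 3 and 11.4 each family's options depend on it and the neurologist receives it. What is missing is the group-level summary.

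The illustration needs both a strong imbalance in counts and a 20-point gap in sensitivity. If sensitivity is unrelated to seizure frequency, pooled and mean per-child values agree in expectation. All of this stands, and it rules out any claim about direction or size.

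It can also be said that one per week is the minimum rate, so the total may exceed 540. That helps only in part. With equal counts the effective number cannot exceed children/ICC however many seizures each child has. For 60 children, 384 is out of reach above ICC 60/384 = 0.16, and 246 above 60/246 = 0.24.

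**Conclusion.** The concern holds as a mismatch between the unit behind the stated precision and the unit of the earlier results, left unresolved by section 10.1. The arithmetic of section 4.4 is correct on its own terms, but its 5-point precision covers only pooled, independent events. Assuming 9 seizures for each of 60 children, it fails at the plan's 384 once the ICC exceeds about 0.05. For a sensitivity of 80% it fails once the ICC exceeds about 0.15, or about 0.07 if 42 children contribute. These thresholds rest on equal counts and an ICC that the documents do not give.

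The documents do not show that the trial is too small, that a pooled result would favour the device, or that a wrong success decision would follow. Reading the per-person results as the natural comparator rests on section 1 and on the per-child decisions in section 3, not on an endpoint definition. The point should be settled before analysis.

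**What to change.** In section 10.1, make the per-child summary the figure set beside the per-person results in section 1: median and IQR of sensitivity, PPV and false alarm rate, with 95% intervals from a bootstrap that resamples children. State how children with no seizures or no alarms are handled. Report pooled values beside these, with an interval that accounts for clustering by child.

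In section 4.4, say that the 5-point figure assumes independent pooled seizures. Restate the precision with the child as the unit, for 60 and for 42 children, over a stated range of within-child correlation.

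If the share of children reaching 80% and 50% is shown, label it descriptive, or estimate it with a model that allows for few seizures per child. It should not be compared directly with the 80% of subjects in section 1.

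The cost is wording in two sections and one more table from data already collected. The downside is a less favourable stated precision and noisy values for individual children: with 9 seizures and 80% sensitivity, the half-width for one child is 1.96 × √(0.8 × 0.2/9) = 26 points.

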# **5 TREATMENT OF SUBJECTS**

Not applicable

**5.1 Investigational product/treatment** 

Not applicable

5.2 Use of co-intervention (if applicable)

Not applicable

5.3 Escape medication (if applicable)

Not applicable

# **6 INVESTIGATIONAL PRODUCT**

Not applicable

6.1 Name and description of investigational product(s)

Not applicable

6.2 Summary of findings from non-clinical studies

Not applicable

6.3 Summary of findings from clinical studies

Not applicable

6.4 Summary of known and potential risks and benefits

Not applicable

6.5 Description and justification of route of administration and dosage

Not applicable

6.6 Dosages, dosage modifications and method of administration

Not applicable

6.7 Preparation and labelling of Investigational Medicinal Product

Not applicable

6.8 Drug accountability

Not applicable

# 7 NON-INVESTIGATIONAL PRODUCT

Not applicable

7.1 Name and description of non-investigational product(s)

Not applicable

7.2 Summary of findings from non-clinical studies

Not applicable

7.3 Summary of findings from clinical studies

Not applicable

7.4 Summary of known and potential risks and benefits

Not applicable

7.5 Description and justification of route of administration and dosage

Not applicable

7.6 Dosages, dosage modifications and method of administration

Not applicable

7.7 Preparation and labelling of Non Investigational Medicinal Product

Not applicable

7.8 Drug accountability

Not applicable

#### 8 METHODS

# 8.1 Study parameters/endpoints

# 8.1.1 Main study parameter/endpoint

#### Performance of the NightWatch:

- Sensitivity;
- Positive predictive value;
- False alarm rate;
- % Time with valid signal allowing proper detection.

# 8.1.2 Secondary study parameters/endpoints (if applicable)

- 1. Validation of remote SDDs (video and audio):
  - Sensitivity;
  - Positive predictive value;
  - False alarm rate;
  - % Time with valid signal allowing proper detection.
- 2. The feasibility of the NightWatch focusing on Acceptability, Demand, Implementation, Practicality, Expansion and Limited-efficacy testing [22].

# **Acceptability**

The parameter Acceptability is defined as:

The extent in which the NightWatch is judged as suitable, satisfying, or attractive for people with epilepsy and their parents/guardians.

# Focusing on:

- Intent to continue use (survey T0)
- Expectations (survey T0)
- Satisfaction (Survey T2 and semi-structured interview with parents/guardians and subjects)

#### **Demand**

The parameter *Demand* is defined as:

The extent in which the NightWatch is likely to be used.

# Focusing on:

Perceived demand (Survey T0)

Version number: 3.0, date April 19, 2018

Actual use (Diary and semi-structured interview with parents/guardians and subjects)

# Implementation

The parameter *Implementation* is defined as:

The extent in which the NightWatch can be successfully delivered to people with epilepsy and their parents/guardians.

# Focusing on:

- Degree of execution, (Diary, semi-structured interview with parents/guardians and subjects and survey T2)
- Success or failure of execution (semi-structured interview with parents/guardians and subjects and survey T2)
- Amount, type of resources needed to implement (semi-structured interview with parents/guardians and subjects)

# **Practicality**

The parameter *Practicality* is defined as:

The extent in which the NightWatch device can be carried out in people with epilepsy and their parents/guardians using existing means, resources, and circumstances and without outside intervention?

#### Focusing on:

- Factors affecting implementation ease or difficulty (semi-structured interview with parents/guardians and subjects and survey T2)
- Positive/negative effects on people with epilepsy and their family members (semistructured interview with parents/guardians and subjects and survey T2)
- Ability of parents/guardians to carry out intervention activities (semi-structured interview with parents and subjects and survey T2)

#### **Expansion**

The parameter *Expansion* is defined as:

The extent in which the NightWatch can provide a new service to people with epilepsy and their parents/guardians.

#### Focusing on:

- Fit with organizational goals and culture treatment of people with epilepsy (group session\* and interview with neurologists)
- Disruption due to expansion component (group session\* and interview with neurologists)

\*At the end of the study, we will evaluate the NightWatch by inviting a group of parents/guardians and professionals to a group session using the value sensitive design methodology.[26]

# **Limited-efficacy testing**

The parameter *Limited-efficacy testing* is defined as:

The extent in which the NightWatch shows a promise of being successful on key intermediate variables (quality of life, stress, sleep, and strain) in people with epilepsy and their parents/guardians.

Focusing on Intended effects of the NightWatch on key intermediate:

- Health-related QoL in people with epilepsy and their parents/guardians, including EQ-5D-5L [27] (Survey T0 and T2)
- Strain and sleep, including Caregiver Strain Index (CSI) [28] and Pittsburgh Sleep Quality Index (PSQI) [29] (Survey T0 and T2).

# 3. Economic evaluation of NightWatch

To evaluate the costs and effectiveness/utility of NightWatch for children and their parents/guardians from a societal perspective.

- Medical Consumption Questionnaire (MCQ) adjusted version (T0 and T2)
  - Questions regarding the subject (to be completed by one or two parent(s)/guardian(s) together)
  - Questions regarding the parent/guardian (to be completed by one or both parent(s)/guardian(s) separately)
- Productivity Costs Questionnaire (PCQ) adjusted version (T0 and T2)
  - To be completed by one or two parent(s)/guardian(s) separately.
- 4. Other secondary study parameters are:
- Compliance as indicated by frequency of use, i.e. hours per night that NightWatch is 'on'.
- Number and nature of interventions due to alarms.
- Effect of algorithm tailoring on performance of the NightWatch.

Table 1: Time schedule of surveys, questionnaires and interviews and feasibility domains.

Time			
period	Method	Duration	Topic
ТО	Surveys T0	10 minutes	
 
Personal/medical information subject and family (baseline)
 
MCQ and PCQ
 
Acceptability:
 
Intent to continue use;
 
Expectations Demand
 
Perceived demand
 

	Questionnaires	30 minutes	Limited-efficacy testing - CSI: Parental strain/stress - PSQI: Parental quality of sleep - EQ-5D-5L: Parental and child quality of life
T1	Diary		Demand - Actual use Implementation - Degree of execution
	Interview (subgroup)	60 minutes	Acceptability - Satisfaction Demand - Actual use Implementation - Degree of execution - Success or failure of execution - Amount, type of resources needed to implement Practicality - Factors affecting implementation ease or difficulty - Positive/negative effects on patients with epilepsy and their family members - Ability of parents/guardians to carry out intervention activities
T2	Surveys T2	10 minutes	
 
MCQ and PCQ         Acceptability
 
Satisfaction         Implementation
 
Degree of execution
 
Success or failure of execution
 
Amount, type of resources needed to implement         Practicality
 
Factors affecting implementation ease or difficulty
 
Positive/negative effects on patients with epilepsy and their parents/guardians
 
Ability of parents/guardians to carry out intervention activities
 

	Questionnaires	30 minutes	Limited-efficacy testing  - CSI: Parental strain/stress  - PSQI: Parental quality of sleep  - EQ-5D-5L: Parental and child quality of life
Optional	Group session	120 minutes	Expansion - Value sensitive design group session

T0 = Before implementation of the SDDs;

T1 = Intervention (2 months); T2= After implementation of the SDDs.

Table 2: Overview of questionnaires

Questionnaire	Domains	No. of items
CSI	Strain related to care provision.	13
	Major domains: Employment, Financial, Physical, Social	
	and Time	
PSQI	Quality of sleep.	10
	Major domains: subjective sleep quality, sleep latency,	
	sleep duration, habitual sleep efficiency, sleep	
	disturbances, use of sleep medication, and daytime	
	dysfunction.	
EQ-5D-5L	Quality of Life.	5
	Major domains: Mobility, self-care, usual activities,	
	pain/discomfort, anxiety/depression.	

# 8.1.3 Other study parameters (if applicable)

Not applicable.

# 8.2 Randomisation, blinding and treatment allocation

Not applicable

#### 8.3 Study procedures

# Inclusion & consent

(See 11.2 Recruitment and consent)

# Run in period

During the first two months, there will be no home-based monitoring. Parent(s)/representative(s) will complete the questionnaires and a subgroup will be interviewed.

